5. DATA MANAGEMENT

5.1 Data collection and management

We will handle and store personal data collected during the study in accordance with the UK GDPR, adhering to the University of Warwick's Data Protection Policy and Information Classification and Handling Procedures, and University of Warwick SOP 15 on Information Handling and Electronic Data Security.

All data in work package 1 will be collected in electronic format: e-mailed signed consent forms, interview recordings, transcripts, researcher fieldnotes, CAQDAS files.

For work package 2 there will be some data collected at the study site initially on paper – signed consent forms, post-event conversation notes, post-event questionnaire. As soon as is reasonably practicable, we will return paper-based documents completed at the study site to the University of Warwick, where they will be saved in electronic format. We will arrange secure transfer of audio and video files recorded during the simulation to an encrypted, password-protected folder on a University of Warwick managed device as soon as is practicable following the simulation, and certainly within 48 hours.

WAST will provide [name] with a link to a secure server to access audio recordings of the 999 calls. [name] will access this server at the University of Warwick and transfer the recordings directly to an encrypted password-protected folder (Symantec PGP encryption) on a secure University of Warwick file server.

There will be video recordings from the drone itself during flight (recorded by SkyBound) and at the simulation site (using a commercial service). These, similarly, will be made available to [name] to access via secure server and to transfer directly to an encrypted password-protected folder (Symantec PGP encryption) on a secure University of Warwick file server. Any original video files showing participants will be deleted as soon as this transfer has been made.

5.2 Data storage

We will keep all data in an encrypted, password-protected folder (Symantec PGP encryption) on a secure University of Warwick file server.

We will store electronic consent forms separately to all other participant documents, in a password-protected subfolder. These will have a numbering system that allows them to be matched to other participant documents in other subfolders, should this be needed. All other participant-related documents will have a number only.

5.3 Data access and quality assurance

Only [name], [name], the senior research fellow and the statistician directly employed to this project will directly access study documents in the encrypted folder. They will only be able to access the study folder after logging in to their University of Warwick accounts via University-managed computers. We will encrypt the study folder using (Symantec PGP Encryption)

If study team members are accessing the folder off-campus, they will first have to have connected to the University's Virtual Private Network.

5.4 Data shared with third parties

We will send an audio recording to an outside commercial transcription service via their secure portal, and we will receive a transcription back from them via the same secure portal. No participant-identifying information will form part of the transcription. We may share fully anonymised data with other members of the study team not primarily based at the University of Warwick for the purposes of quality assurance and review. We may make fully-anonymised datasets available as part of any peer-reviewed publication, according to the requirements of that journal. We will not share any data with any other third party. We will not share individual case data or any personal identifiable data at any time.

5.5 Archiving

We will hold personal identifiable information, including the names, email addresses and/or phone numbers of participants until the end of the study. We will hold personal data on consent forms only until the peer-reviewed scientific articles are published, in case a participant wishes to withdraw their consent. We anticipate that this will be a maximum of 12 months after the end of the study, and we will securely delete this personal data earlier if possible. All personal identifiable data will be securely stored in a password protected folder on the University of Warwick server and accessed only by authorised study personnel. We will retain all other study data on the University of Warwick server for at least ten years from the date of any publication based upon this study, in line with the University's Research Data Management Policy:

https://warwick.ac.uk/services/ris/research_integrity/code_of_practice_and_policies/research_code_of_practice/datacollection_retention/research_data_mgt_policy

Only [name] will have access to this data, if required, after peer-reviewed publication. He will be responsible for its storage and eventual deletion. Encryption programmes provided by the University can securely remove this data and we will seek advice from IT Services about the best way to do this at that time.

6. STUDY ORGANISATION

6.1 Sponsorship arrangements

The University of Warwick will sponsor this project.

6.2 Collaborators

This project is a collaboration between the University Hospitals Coventry and Warwickshire NHS Trust, University of Warwick, Welsh Ambulance Service NHS Trust and SkyBound Rescuer.

6.4 Ethical and regulatory approvals

We are seeking NHS Research Ethics Committee (REC) and Health Research Authority (HRA) approvals for this project, and this protocol accompanies an Integrated Research Application System (IRAS) application.

Interview participants (work package 1) are NHS service users, being recruited because they intervened at an out-of-hospital cardiac arrest and likely interacted with an NHS ambulance service on a 999 call and/or at the scene. No flying will take place without permissions from the CAA.

6.5 Indemnity and insurance

NHS indemnity covers NHS staff, medical academic staff with honorary contracts, and those conducting the trial. NHS bodies carry this risk themselves or spread it through the Clinical Negligence Scheme for Trusts, which provides unlimited cover for this risk. The University of Warwick provides indemnity for any harm caused to participants by the design of the research.

Drone-specific issues

SkyBound Rescuer has operational authorisations from the UK CAA to fly unmanned aircraft, with a flying weight of less than 25kg. SkyBound Rescuer will provide drone pilot(s), who will be fully licensed and accredited.

SkyBound Rescuer has Public Liability Insurance (worldwide) for up to £10 million for the duration of this project. An Operational Safety Case detailing all activities in this project has been submitted to the CAA, and no flying will take place without their express approvals.

The drone has two cameras. The first is a 'First Person View' camera that is always forwards facing and so cannot identify people or personal information on the ground. The second is downward facing and allows the drone operator to see that the lowering zone is clear of people and obstructions. The camera resolution is such that individual people and personal information (e.g. number plates, house numbers) are not identifiable.

6.6 Study timeline

This project is funded for 18 months. **Appendix 4** shows a GANTT chart detailing the study timeline.

6.7 Administration

The NIHR have issued a research contract to University Hospitals Coventry and Warwickshire (UHCW) NHS Trust, who have arranged collaboration agreements with WAST and with University of Warwick. The University of Warwick have administered the relevant commercial subcontract with SkyBound Rescuer.

6.8 Funding

This project has received funding from Competition 47 of the NIHR RfPB scheme (ref: NIHR204382). We will also receive funding for Excess Treatment Costs from Health and Care Research Wales (HCRW).

6.9 Essential documentation

We will store all study material in an encrypted, password-protected folder on secure servers at the University of Warwick in line with the University of Warwick SOP 11 (Essential Documentation: Creation and Maintenance of Trial Master and Investigator Site Files), and with advice from the Quality Assurance Team at Warwick Clinical Trials Unit.

6.10 Intellectual Property

The project will be using and testing SkyBound Rescuer's background IP, as outlined in this table:

Description of Background IP	Owner	Nature of Restriction	Risk to Research & Outcomes
SkyBound Coordinator platform: software platform that manages the end-to-end process of data-driven public safety drone missions	SkyBound Rescuer	Nil	Nil
SkyBound Requestor platform: software portal to request a drone mission	SkyBound Rescuer	Nil	Nil
SkyBound Remote Viewer Portal: portal for remote viewers to monitor the drone's feed and location and interact with the live feed	SkyBound Rescuer	Nil	Nil
SkyBound Manager platform: software platform that catalogues/manages ground risks, air risks, installation, and maintenance for a drone network	SkyBound Rescuer	Nil	Nil
Training standards & materials for using each SkyBound platform	SkyBound Rescuer	Nil	Nil
5-Phase BVLOS methodology: a step by step process for achieving BVLOS permission from the CAA	SkyBound Rescuer	Nil	Nil
Mission planning algorithm for drone defib deliveries, inc. flight parameters & configuration details produced by SBR research	SkyBound Rescuer	Nil	Nil
Design spec for an automated drone defib delivery system	SkyBound Rescuer	Nil	Nil
CONOPS and Operations Manuals for public safety drone applications	SkyBound Rescuer	Nil	Nil

Foreground IP is owned by the Contractor except for: the Operational Safety Case for Beyond Visual Line of Sight which will be owned by SkyBound Innovations Ltd.

Research Data is owned or controlled by the Contractor. The contractor will put into place data sharing arrangements as necessary so that relevant Foreground IP arising as a result of this project can be used by collaborators for the purposes of dissemination, education and as a basis for future related research.

7. DISSEMINATION AND IMPACT

Our audiences are patients and the public, clinicians, and policy makers (including NHS and UK ambulance service leaders). We will involve all study team members, including our PPI members, to:

- produce written summaries and infographics for both lay and professional audiences
- Disseminate our findings via open-access peer-reviewed publications (one for the findings of each work package), podcasts, blogs, national and international conference presentations and social media
- Use public relations teams from the University of Warwick, WAST, regulatory agencies and SkyBound to assist in dissemination of our findings according to their current procedures
- Engage policy makers through our existing relationships with key organisations (e.g. International Liaison Committee on Resuscitation, European Resuscitation Council, Resuscitation Council UK, British Heart Foundation).

9. APPENDICES

Appendix 1 – Sensitive Call Action flowchart

Appendix 2 – Post-event questionnaire (work package 2)

PARTICIPANT NUMBER _____

You have just retrieved a defibrillator delivered by a drone. Regarding this (please tick the relevant box):

1. I found it unnecessarily complex.

Strongly
disagree

Strongly
agree

1	2	3	4	5

2. I thought it was easy to do.

Strongly
disagree

Strongly
agree

1	2	3	4	5

3. I felt very confident doing this.

Strongly
disagree

Strongly
agree

1	2	3	4	5

4. I would imagine that most people would be able to do this.

Strongly
disagree

Strongly
agree

1	2	3	4	5

Appendix 3 – Post-event conversation questions (work package 2)

PARTICIPANT NUMBER _____

Age (in years) _____

Gender (M, F, identifies another way – specify) _____

Training in last five years (Yes/No)

CPR only _____

AED only _____

Both _____

Real-world experience in last five years (Yes/No, number of occasions if yes)

CPR only _____

AED only _____

Both _____

Opening question:

- “What are your thoughts on how that went?”

Probing questions (if needed):

- “Did you encounter any difficulties in retrieving the defibrillator?”
- “Is there something that would make it easier for you to retrieve the defibrillator”

Closing question:

- “Is there something else you would like to add to your answers so far?”

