3.2 Approach and rationale

There is work in simulation studies suggesting that bystanders generally find it easy to interact with a drone that has delivered an AED to them (12, 17-19). In our previous simulation work participants experienced a few common issues (19), many of which involved their interaction with the 999 call-handler. They often felt uncertain about when it was safe to leave the patient to retrieve the AED, or felt uncomfortable in leaving the patient, despite audible prompts from the drone to indicate that it was indeed safe. They relied on feedback or 'permission' from the call-handler to allow them to do this. There were also difficulties in interacting with the AED itself – which has automated voice instructions helping people to use it – when 999 call-handler instructions conflicted and when the noise of the departing drone made it difficult to hear instructions.

There is a need to investigate further the behaviours of people who have used or who may use an AED at an out-of-hospital cardiac arrest, particularly with regards to how they interact with the 999 call-handler.

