4.3 Approach and rationale

Demonstrate an AED drone-delivery system that is fully integrated with ambulance service systems, in 'end-to-end' BVLOS flights for simulated out-of-hospital cardiac arrests.

We have previously demonstrated that study participants can interact with a drone-delivered AED (19). What has not been tested before in the UK is a fully-integrated system that allows the BVLOS delivery of an AED via drone following diagnosis of cardiac arrest during a 999 call.

In this work package, we will ask study participants to come to the aid of simulated out-of-hospital cardiac arrest patients and to call '999'. The call will be directed to a WAST training call centre, which operates in the same way as a real 999 call, and used by us in our previous simulation study (19). In all other regards, the processes demonstrated in this work package (cardiac arrest diagnosis, automated drone activation, drone flight, real-time communications between drone and Emergency Operations Centre, AED delivery) will occur as they would in a real-world scenario.

When delivering an AED via drone, one important consideration is how long it takes a bystander to retrieve and attach the AED. Unnecessary delays in performing CPR can be detrimental to patient outcome, but potential delays caused by retrieving and using an AED must be balanced against the potential benefits of early defibrillation. Not all

patients in cardiac arrest will be suitable for defibrillation. It is not possible to know this in advance – an AED performs heart rhythm analysis and then shocks / does not shock according to its findings. Knowing how quickly a shock can be delivered and how long a bystander has to spend away from a patient to retrieve an AED will be an important consideration when implementing effective drone-delivered AED systems in the future.

Our previous simulation study demonstrated the importance of the bystander / 999 call-handler interaction in the process of retrieving and using a drone-delivered AED. This study will use information from audio/video analyses and from conversations to help ambulance services determine how best to communicate information about the arriving drone, and how best to offer advice during the 999 call about using an AED effectively.

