4.7 Analyses

We will report timings and score from the questionnaire based on the System Usability Scale using median and interquartile range.

The study team will review other data collected during the study itself:

- Audio recordings of 999-calls and voice/text interactions between drone pilot and 999 call-handler.
- Video from the drone itself during flight.
- Video from the scene of participant interaction with drone and AED.

- Feedback from 999-call-handler and drone operator.
- Real-time observations and field-notes about the out-of-hospital cardiac arrest simulations.

We will review participant feedback and on-site observations after each flight session to identify any critical issues before subsequent sessions. We will collate the summated information following the simulation to identify key themes related to: drone activation process, real-time in-flight communications between drone and ambulance service, and interaction between bystander and drone. Our aim is to iteratively improve the integrated drone-dispatch process throughout the study period, and in preparation for future flight operations for real-life out-of-hospital cardiac arrests.

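### Work package 2 relies on participant conversations to learn how call-handlers should communicate and advise, but its only written probes, its questionnaire and its named themes do not ask about this

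*Protocol*

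**What the plan says.** Protocol section 4.3 gives the reason for looking at the call: "Our previous simulation study demonstrated the importance of the bystander / 999 call-handler interaction" in retrieving and using the AED. It then commits WP2 to "use information from audio/video analyses and from conversations to help ambulance services determine how best to communicate information about the arriving drone", and to the further question of "how best to offer advice during the 999 call about using an AED effectively". Conversations are therefore one of two named kinds of source for both questions.

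Section 3.2 describes what was found before: participants had a few common issues, "many of which involved their interaction with the 999 call-handler". They were unsure when it was safe to leave the patient, looked to the call-handler for permission, and sometimes received call-handler instructions that clashed with the AED's own.

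The WP2 post-event instruments are set out in the appendices:

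- **Appendix 2** (questionnaire) opens with "You have just retrieved a defibrillator delivered by a drone" and asks four rated items about that act.
- **Appendix 3** (conversation) has an open opening question, two probes to be used if needed, and an open closing question. The probes are "Did you encounter any difficulties in retrieving the defibrillator" and "Is there something that would make it easier for you to retrieve the defibrillator".

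Section 4.7 says the collated information will be used to find themes on "drone activation process, real-time in-flight communications between drone and ambulance service, and interaction between bystander and drone".

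**The concern.** The rationale asks how the call-handler should communicate and advise. The prompts ask how retrieval went. If a participant says nothing about the call-handler, the conversation record alone cannot show whether there was no difficulty or whether the topic never came up.

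Simulation participants are the only bystanders in the project who experience the integrated system, including drone information relayed live through the call-handler. Section 4.4 plans to correct critical issues between flight sessions using participant feedback as well as audio/video review, so an unprompted topic may also be missed while it could still be acted on. Views not sought straight after the simulation cannot readily be recovered later.

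**Working it through.** The protocol states no figure on this point and no formula applies. The check sets each instrument against the purpose in section 4.3.

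| Element | Count | About retrieval | Names the call-handler | Names attaching or using the AED |
|---|---|---|---|---|
| Appendix 2 rated items | 4 | 4 | 0 | 0 |
| Appendix 3 probes | 2 | 2 | 0 | 0 |
| Total prompted items | 4 + 2 = 6 | 6 | 0 | 0 |
| Appendix 3 open questions | 2 | no topic named | no topic named | no topic named |

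1. **Questionnaire.** The four items (complexity, ease, confidence, whether most people could do it) contain no object of their own. Each takes its meaning from the stem, which is retrieval.

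2. **Probes.** Both name retrieval. They are also conditional, so even these need not be put to everyone.

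3. **Scenario.** Under section 4.4 the simulation continues past retrieval to attaching the AED and delivering one shock, with the call-handler involved. The stated objective also runs from the 999 call to AED use. The prompted items stop at retrieval.

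4. **Themes.** Section 4.7 names three: drone activation, communication between drone and ambulance service, and bystander with drone. The pairing that section 4.3 singles out, bystander with call-handler, is in 0 of the 3.

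5. **Other sources.** These were checked for whether they fill the gap:
   - The 999-call audio and scene video (section 4.7) record what was said and done, including hesitation and requests for permission. They do not reliably show what was understood or wanted.
   - Call-handler feedback and field notes (section 4.7) are accounts by other people.
   - WP1 interviews (section 3.3) ask directly about the call-handler, including for a drone-delivered AED, in approximately 24 people. They are a separate group, asked about their likely reaction to drone delivery, who did not experience this system.

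6. **Numbers available.** WP2 plans 20 participants over up to four flight sessions. If all four are used and filled evenly, that is 20 / 4 = 5 per session. With about five conversations to review before the next session, volunteered remarks on any one topic may be few.

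**The case against.** **Several objections have force.**

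- Section 4.3 does not rest on conversations alone. The recordings, WP2 timings, field notes and call-handler feedback all bear on the call. This stands, and it limits the size of the point.
- The opening and closing questions are open, so participants can raise the call-handler. This stands; what is missing is a topic-specific prompt, not the opportunity to comment.
- Retrieval and the call are linked. By design the call-handler says when it is safe to approach, and section 3.2 places the earlier uncertainty at the moment of leaving to fetch the AED. A probe about difficulty in retrieval may well draw this out. This stands in part: it does not extend to advice on attaching and using the AED, where the gap is clearest.
- Section 4.6 reuses the approach of the previous simulation study, which did bring call-handler problems to light. That is reassuring, but the protocol does not say whether they emerged from conversations or from observation.
- The open style is deliberate, and the call-handler aim appears in the rationale and is not listed as a WP2 objective. This argues for few and short additions.

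**Two stronger readings are not supported.** A reader might infer that the project collects no prompted participant data on the call-handler. WP1 does so explicitly, so the statement can apply only to WP2 post-event feedback. A reader might also infer that the earlier study placed most difficulties in the call-handler interaction; section 3.2 says many, of a few common issues.

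**Conclusion.** The mismatch is real and moderate. None of the six prompted WP2 items and none of the three named themes addresses the interaction between bystander and call-handler, and no prompted item addresses attaching or using the AED, although section 4.3 names the conversations as a source on both. Simulation participants' own views on these matters therefore depend largely on what they volunteer.

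This does not mean that the study will leave the communication question unanswered: other WP2 sources and WP1 cover it in part. Timings and questionnaire scores are unaffected. The conclusion assumes that the conversation follows Appendix 3 as written; an interviewer who routinely asked about the call would narrow the gap, but the protocol does not provide for that. It is best treated as a cheap improvement.

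**What to change.** In Appendix 3, after the open opening question, add two short probes put to every participant:

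1. Whether the call-handler's information about the drone, and about leaving the patient, was clear and came at the right time.
2. How attaching and using the AED went while on the call.

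Keep the opening question first, so that spontaneous comments are recorded before any prompt. In section 4.7, add interaction between bystander and 999 call-handler as a fourth theme.

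**Cost.** One appendix and one sentence of section 4.7 change. The conversation becomes slightly more directed and a little longer. The protocol gives no time per question, so the added time cannot be computed. It must fit the existing limits: 5 minutes for the conversation, which already includes demographics, training and experience, and 15 minutes for conversation and questionnaire together. No extra participants are needed.
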